Accessing Prenatal and Labor/Delivery Data. After study completion, with subject's HIPAA authorization, we will access their medical record data for prenatal (e.g., gestational weight gain, diagnosis of gestational diabetes, complications, etc.) and labor/delivery data. A subject can choose to not allow us to have access – and she can decide to provide the health information she wants to share. A study staff member will work with the subject's OBGYN provider to coordinate access to this data (e.g., electronic medical record access or hard copy of the prenatal and labor/delivery data).

Visit D Postpartum Assessment and Weekly Measurements At 6-8 weeks postpartum, women will return to Noll Lab to complete maternal and infant measurements; they will be expected to bring their infant with them to this session but if they do not want their infant involved, they will still be asked to complete the measurements asked of them. Women will be asked to (1) weigh themselves using the Aria Wi-Fi scale for a 7-day period, (2) wear the Jawbone wrist-worn activity monitor for a 7-day period, (3) complete one Breezing device measurement, (4) provide one urine sample, (5) one BodPod assessment, and (6) take photographs of their food for 2 weekdays and 1 weekend day. While on site, the women's babies will (1) complete a PeaPod measurement. The baby's test takes place in a similar small space with a window where the baby can be seen the entire time. The baby's test is two minutes long, and typically only one test is needed. We can stop the test at any point. The baby will be placed in the warm measurement space free of any clothing or blankets. The PeaPod measurement is similar to the BodPod measurement.

Postpartum Survey Women will be emailed a link to a postpartum survey 2-6 weeks after delivery. Women will complete this survey on REDCap. Women without access to the Internet will be sent the survey via the mail. The survey has been uploaded as study materials.

- R56: The additional normal weight (body mass index 18.0-23.9) subjects will be assigned to the control group (i.e. will not be randomized); these subjects will complete all measures to expand data collection of indicators of fetal growth as well as self-report data.

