1.0 Objectives

1.1 Study Objectives

Purpose: The proposed overall research aims to establish feasibility of delivering an individually-tailored, behavioral intervention to manage gestational weight gain [GWG] that adapts to the unique needs and challenges of overweight/obese pregnant women [OW/OBPW] and will utilize control systems engineering to optimize this intervention; in other words, make this intervention manage GWG in OW/OBPW as effectively and efficiently as possible.

Aim 1: This application is to conduct the second study of the research plan (Study 2) to (a) test an individually-tailored behavioral intervention (including components of physical activity, healthy eating, goal-setting, self-monitoring, and GWG management) with decision rules for when and how to adapt dosages for an individual and (b) the randomization, participant retention, and data collection procedures with an intervention (treatment) and control groups in a cohort of OW/OBPW from approximately ~6-35 weeks gestation; with follow-ups through delivery to 6-weeks postpartum. We hypothesize that women in the intervention group will have more positive eating and activity behaviors and psychosocial and behavioral outcomes as well as manage their GWG better compared to controls.

Aim 2: R56: To prospectively characterize the effects of the intrauterine environment on fetal growth and infant birth weight. Detailed, prospective data collection on Healthy Mom Zone participants offers the novel opportunity to (a) assess how the intrauterine eating and physical activity environment impacts fetal growth and (b) explore the effects of our GWG intervention on fetal growth and infant weight. We hypothesize that by changing the maternal prenatal eating/physical activity environment, a critical time in the lifecycle, we will observe differences between intervention and control mother-infant dyads on in utero markers of fetal growth and

infant birth weight. R56: In addition, we will explore how individual differences in maternal sleep duration, hydration, and stress impact fetal growth and development and infant birth weight.

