2.3 Study Rationale

The research proposed here will establish the dosage of components needed to impact GWG and develop an efficient (optimized) intervention to effectively manage GWG in OW/OPBW before a randomized controlled trial (RCT) can be implemented.

Rationale for expanding recruitment to normal weight (body mass index 18.0 to 23.9) women: this control-only alternative will be offered to women who are not eligible for the intervention study because their body mass index is below the current cut-off of 24.0. The purpose of extending the control group is to fulfill the target enrollment for the ancillary grant (1R56HL126799-01).

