8.2 Statistical methods

Biostatistician, Co-I [name], will be responsible for coordinating data management and statistical design/analyses aspects required for feasibility studies including data cleaning, analytical set construction, documentation, analyses, and preparation of data summaries for reporting purposes. He will provide leadership in designing/formatting data collection forms to reduce data collection/recording errors and develop a well-defined/comprehensive data quality assurance program to ensure complete, accurate, and valid data, while limiting variability in data collection/recording. Study data will be managed using REDCap (Research Electronic Data Capture), is a secure web application designed to support data capture for research studies, providing user-friendly web-based case reports, real-time data entry validation (data types/range checks) audit trails, and a de-identified data export mechanism to statistical packages (SPSS, SAS, Stata, R/S-Plus). **Analysis Plan.** Study 2 is to establish feasibility; descriptive statistics, including means/standard deviations (continuous variables) and frequencies (categorical variables) will be used to characterize the data. Study 2 will provide estimates for the primary endpoint (GWG) to power a future RCT. Linear mixed-effects models will be used to assess differences between intervention and control groups with respect to changes in continuous outcomes over time (from pre- to post-intervention; daily/weekly) on GWG and related health outcomes. Generalized estimating equations with a logit link will be used to assess differences between intervention and control groups for dichotomous outcomes over time. Because this is a

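### Section 8.2 does not limit intervention-versus-control comparisons to the randomised women, although up to 20 non-randomised normal-weight women are assigned to the control group; Aim 2 is the most exposed

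*Combined protocol and SAP*

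**What the plan says.** The last bullet of section 6.2.1 states: "The additional normal weight (body mass index 18.0-23.9) subjects will be assigned to the control group (i.e. will not be randomized". It adds that "these subjects will complete all measures to expand data collection of indicators of fetal growth as well as self-report data". Other sections use the same label. Section 3.1 admits these women as controls who cannot receive the intervention, section 15.0 counts 20 more control subjects, and section 16.2 sets the number at up to 20. Section 2.3 gives the reason: "The purpose of extending the control group is to fulfill the target enrollment for the ancillary grant".

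Section 8.2 sets out the group comparison: "Linear mixed-effects models will be used to assess differences between intervention and control groups with respect to changes in continuous outcomes over time". Dichotomous outcomes get the same comparison by generalized estimating equations with a logit link. No analysis set is defined, no restriction to randomised women is given, and no BMI or cohort term is named. Building analysis sets appears only as one of the biostatistician's duties. The section also says that "Study 2 will provide estimates for the primary endpoint (GWG) to power a future RCT".

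Aim 2 in section 1.1 has as part (b) to "explore the effects of our GWG intervention on fetal growth and infant weight". Its hypothesis is that "we will observe differences between intervention and control mother-infant dyads on in utero markers of fetal growth". It does not say which controls count.

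**The concern.** The document uses one term, control group, for two kinds of women. Some are overweight or obese women randomised to control. The others are normal-weight women placed there because they could not be randomised. Section 8.2 uses the term without saying which is meant, so an analyst who applies 6.2.1 and 8.2 as written would put both kinds on the control side.

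That would lose the protection of randomisation. The intervention women would be compared with a control group made up largely of women in a BMI band that no intervention woman can occupy. Maternal BMI would then be confounded with group in an analysis meant to show what the intervention does to fetal growth and infant weight.

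**Working it through.** **1. The plan's own figures.** Section 8.1 takes 12 per group and 20% dropout: 12 / (1 − 0.20) = 15 per group, and 2 × 15 = 30. Section 15.0: 30 + 50 + 6 + 20 = 106. Both reproduce and neither is in dispute. The 8.1 calculation covers only the 30; the 20 extra women appear only in the overall count.

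**2. The control group taken literally.** Inputs: 15 randomised controls (8.1), up to 20 normal-weight women (16.2), 20% dropout (8.1). Let f be the non-randomised share of controls.

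| Case | Randomised controls | Added women | f |
|---|---|---|---|
| As enrolled | 15 | 20 | 20/35 = 57% |
| Both lose 20% | 12 | 16 | 16/28 = 57% |
| Only randomised controls lose 20% | 12 | 20 | 20/32 = 62.5% |
| Only 10 added women enrol | 15 | 10 | 10/25 = 40% |

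The enrolled contrast is 15 against up to 35, instead of 15 against 15.

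**3. What pooling would do.** For an unadjusted difference in means, let δ be the true effect, C the mean in randomised controls and N the mean in normal-weight women. The expected contrast is δ − f × (N − C). With f = 0.57, 57% of any difference between the two kinds of control enters the estimated effect. The documents give neither N nor C for fetal growth or birth weight, so the product cannot be evaluated.

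**4. Whether a BMI covariate would help.** Section 3.1 sets BMI at 24 or more for the intervention study and 18.0 to 23.9 for the added women. No intervention woman has a BMI in the added women's range. A BMI term would therefore rest on extrapolating the BMI–outcome relation across the boundary at 24.

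**5. Which comparisons the text limits to the randomised women.**

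- GWG: Aim 1 and section 6.1 place the two groups in an overweight or obese cohort. Visit A takes thirty such women to the assessment that precedes randomisation. Section 8.1 ties the mean and variance for the future RCT to 15 per group. Appendix A sets gain targets only for overweight and obese women. The intended set is clear from context, though 8.2 does not state it.
- Fetal growth and infant weight: Aim 2 draws on the study's participants generally and names no BMI range or randomised subset for its dyad contrast. Aim 2 is labelled R56, and the extra women were recruited to meet that grant's enrolment. The text gives an analyst a reason to include them and none to exclude them.

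**The case against.** The strongest reply is that pooling is nowhere stated and the context argues against it. Section 8.2 directly follows 8.1, which describes two groups of 15. Section 2.3 says that "this control-only alternative will be offered to women who are not eligible for the intervention study", which separates them from the trial, and 6.2.1 itself flags them as not randomised. This stands for GWG. A reader might infer that the primary endpoint, or the estimates passed to the future RCT, will be contaminated; the documents do not support that. For GWG only the explicit rule is missing.

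A second reply is that 8.2 never names fetal growth or birth weight, that Aim 2(b) is exploratory, and that the stated R56 modelling can use a wider BMI range. It is correct that 8.2 reaches Aim 2 only through its mention of related health outcomes. But Aim 2 still states a group contrast, and no other section says who is in it. Including the women in the dynamical models is not a defect; counting them as controls in an intervention contrast would be.

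A third reply is that this is a pilot whose tests are to be read with great caution. Caution about tests does not remove bias from estimates, and 8.2 makes estimation its main purpose. It does mean that no confirmatory conclusion is at stake.

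A reader might also try to size a GWG bias from the recommended gain ranges in section 10.2. Those ranges are recommendations, not observed gains, and the sign of the result depends on what each group is assumed to gain. Appendix A also says GWG will be standardised to BMI-based targets. No reliable figure follows.

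**Conclusion.** The plan is wrong as written in one respect: its literal definition of the control group includes women who were never randomised, and 8.2 does not exclude them from the group comparisons. The exposure lies mainly in Aim 2. Confidence is moderate, because pooling is permitted by the wording rather than stated, and because the ancillary grant's analysis plan is not in the documents.

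At full enrolment of the extra women, 57% of enrolled controls would be non-randomised. This is not a ceiling: it becomes 62.5% if only the randomised controls lose 20%, and it falls to 40% if only 10 extra women enrol. The confounding by BMI would be structural, with no overlap between intervention women and added controls. The size and direction of the resulting bias in fetal growth or birth weight cannot be derived from the documents. This should be fixed before analysis.

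**What to change.** In section 8.2, state that all intervention-versus-control comparisons under Aims 1 and 2, and the GWG mean and SD used for the future RCT, include only the randomised overweight or obese women, analysed by assigned group.

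In section 6.2.1, describe the normal-weight women as a non-randomised reference cohort. Report them separately, and use them in the R56 association and dynamical models with BMI included. Label any contrast that includes them as non-randomised and secondary; this also covers the possibility that the ancillary grant calls for one.

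The cost is one sentence and a change of label; the 30 randomised women and the data collection are unaffected. The Aim 2 contrast would have 15 rather than up to 35 controls. With equal variances the variance factor goes from 1/15 + 1/35 = 0.095 to 1/15 + 1/15 = 0.133, a ratio of 1.4. The standard error is then larger by √1.4 = 1.18, or about 18%. That precision is worth giving up, because it would be bought with a confounded comparison.

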6.3 Duration of Participation

Visit A Pre-Intervention Assessment: 120 minutes (can be split into two 60-minute sessions or if participants choose, can be one 120 minute session).

Visit B Intervention Sessions: For those in the intervention group, they will be participating in one 30-min/week education session. Given the adaptive “step-up dosage” nature of this intervention, participation will increase as the dosage increases, *ranging from 1 day per week of 30-min to up to 4-days/week for 150 minutes plus 10-30 min/week of guided instructor feedback.*

Visit C Post-Intervention Assessment: 60 minutes for the interview and 20 minutes for the postpartum survey.

7.0 Data and Specimen Banking

7.1 Data and/or specimens being stored

Blood specimens will be stored a -80°C freezer. Urine samples will be stored in a -20 °C freezer.

7.2 Location of storage

Specimens will be stored in a -80°C -20 °C and freezer space located in the Clinical Research Center.

7.3 Duration of storage

All biological samples except whole blood will be transported to designated locations/laboratories for analyses on the same day as collection,

7.4 Access to data and/or specimens

Freezers are kept in a locked room. Only research staff will access the biological samples.

7.5 Procedures to release data or specimens

Frozen samples will be shipped on dry ice to selected laboratories for analysis the same day as collection, either delivered by research technician to local laboratories or by using a company compliant with biohazard safety protocols for shipping. Laboratories will be sent biological samples with a participant ID# (we will not be sending personally identifying information). All laboratory results will be identified by participant ID# only.

7.6 Process for returning results

Since the blood work and urine samples are non-diagnostic, we will not be sharing the results with the participants unless otherwise asked for.

8.0 Statistical Plan

8.1 Sample size determination

For Study 2, Julios⁵⁰ effectively argues a sample size of 12 per group is adequate to assess feasibility, address regulatory considerations, and obtain sufficient precision of the mean and variance to perform a formal sample size and power calculation for the future RCT. The primary endpoint of the future RCT will be powered on GWG. Factoring in an anticipated 20% subject drop-out based on our pilot work,⁵⁰⁻⁵² we will recruit a total of 30 subjects (i.e., 15 per group).

48. Symons Downs, D. (2011). Determinants and outcomes of physical activity in pregnancy: Findings from Active MOMS, a randomized physical activity intervention for pregnant women. *Annals of Behavioral Medicine*, 41, S135.
50. Julios, S. A. (2005). Sample size of 12 per group rule of thumb for a pilot study. *Pharmaceutical Statistics*, 4, 287-291.

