pilot study, the primary focus of these analyses is for parameter estimation; any hypothesis test will be interpreted with extreme caution to guide the future RCT as this pilot study is deliberately not powered to make definitive claims. All modeling development and simulation will be done in Matlab with SIMULINK and the use of functional data analysis modeling for time-varying modeling will rely on SAS. **Participant Dropout & Other Missing Data.** While every attempt will be made to collect complete data and prevent participant dropout, missing data are inevitable. We have inflated the sample size for Study 2 as described above. We will compare characteristics of those with missing data to those with complete data. These feasibility studies will provide valuable information to minimize missing data in the future RCT (e.g., they will help determine reasons for drop-out, assess which methods for data collection need to be modified/changed, examine data collection and retention of the control group, etc).

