15.0 Number of Subjects

Study 2: target = 30 + anticipated 50 screened failures + 20% dropout (6) + 20 additional control subjects = 106

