16.2 Feasibility of recruiting the required number of subjects

For Study 2, we will recruit 30 OW/OBPW who meet the eligibility requirements. We do not anticipate any issues with retaining this sample for the study. We will use our past experience with recruiting/retaining pregnant women to recruit OW/OBPW for the proposed research. The PI, [name], has years of experience recruiting pregnant women and recruited 127 pregnant women into the Active MOMS RCT, DK07586702 (52% pre-pregnancy OW/OB; <5% drop-out) from State College, PA. MNPG OBGYNs patient population is large and contributes to the >1,200 births per year at MNMC. We were also successful with recruiting our target of 24 participants for study 1 in CATS 00000122.

R56: For the study 2 extension of control subjects, we will recruit up to 20 additional normal weight women who meet the eligibility requirements.

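### Section 15.0 adds a 20% drop-out allowance to a target of 30 that section 8.1 has already inflated for drop-out, so the number to be randomised is 30 in one place and up to 36 in another

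*Combined protocol and SAP*

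**What the plan says.** Section 8.1 (Sample size determination) relies on a published rule of thumb that "a sample size of 12 per group is adequate to assess feasibility". It continues "Factoring in an anticipated 20% subject drop-out based on our pilot work" and concludes "we will recruit a total of 30 subjects (i.e., 15 per group". In section 8.2, the paragraph on drop-out and missing data says "We have inflated the sample size for Study 2 as described above".

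Section 15.0 (Number of Subjects) gives "Study 2: target = 30 + anticipated 50 screened failures + 20% dropout (6) + 20 additional control subjects = 106".

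Section 16.2 says "For Study 2, we will recruit 30 OW/OBPW who meet the eligibility requirements". Section 6.2.1 likewise brings thirty overweight/obese women to the pre-intervention assessment. Neither mentions a further 6.

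Two other passages bear on the point. Section 3.3.2 says that withdrawn randomised women will be replaced according to the randomisation scheme, and gives no number. Section 16.2 describes an earlier randomised physical activity trial of 127 pregnant women as "52% pre-pregnancy OW/OB; <5% drop-out".

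**The concern.** In section 8.1, 30 is the number after the drop-out allowance. In section 15.0, 30 is the number before it. Both cannot be true of the same figure, and the plan does not say which governs enrolment.

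What is at stake is the planned size of the randomised cohort and the total enrolment figure. If section 15.0 is followed, up to six more pregnant women enter than the sample-size section calls for, and the stated basis of 12 completers per group no longer describes the trial being run. Retention is also one of the things this feasibility study sets out to test (Aim 1), and poor retention is a listed ground for stopping (section 10.8). The planning rate and the way it is applied should therefore be clear.

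**Working it through.** **Inputs.** 12 per group, 20% drop-out and 30 recruited come from 8.1. The statement that inflation has already been applied comes from 8.2. The 50 screen failures, 6 for drop-out, 20 additional controls and total of 106 come from 15.0. The under-5% drop-out in one earlier trial comes from 16.2.

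**Step 1: reproduce 8.1.** Inflation is n/(1 − d).
- Per group: 12/(1 − 0.20) = 15.
- Total: 24/(1 − 0.20) = 30.

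This matches exactly, so 12 per group, 20% and 30 are consistent with one another.

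**Step 2: reproduce 15.0.**
- 30 × 0.20 = 6.
- 30 + 50 + 6 + 20 = 106.

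The sum is right, but the 30 in it is the inflated figure from step 1. The implied maximum of overweight/obese women is 30 + 6 = 36.

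**Step 3: look for a reading under which both sections agree.**
- If 30 is the number randomised, 20% loss leaves 30 × 0.80 = 24, which is 12 per group as in 8.1. The 6 is then not needed, and the total is 30 + 50 + 20 = 100.
- If 30 is the number of completers, the method in 8.1 gives 30/0.80 = 37.5, rounded up to 38, not 36. It also contradicts 8.1, where the completers are 24.
- If 36 are randomised, 20% loss leaves 36 × 0.80 = 28.8, which is neither 24 nor 30. Going from 36 to 24 means a 33% loss (1 − 24/36); going from 36 to 30 means 16.7% (1 − 30/36).
- If the 6 are replacements who themselves drop out at 20%, expected completers are 24 + 6 × 0.80 = 28.8, again about 29.

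No reading makes 8.1 and 15.0 agree as written.

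**Step 4: trace the 20%.** The superscript in 8.1 is 50–52. The list under that section runs from 47 to 50, and item 50 is the rule-of-thumb paper, so the superscript does not lead to pilot work. Items 47–49 are the team's own papers, and item 48 names the earlier physical activity trial. The only earlier drop-out rate shown anywhere is the under-5% for that trial. None is given for item 49, which is a different study, or for Study 1.

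**The case against.** The strongest defence is that section 15.0 is a head count, not a sample-size statement. It also includes screen failures, and section 3.3.2 provides for replacement, so the 6 could be an upper limit on replacements for an expected six losses among 30. That is plausible, and deleting the 6 without thought could remove room that 3.3.2 needs. It does not remove the conflict. Section 15.0 labels the 6 as drop-out, not replacement. If replacement is meant, inflation and replacement both cover the same losses, and the 30 recruited in 8.1 still differs from an implied 36.

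It can also be said that the effect is small and that section 8.2 calls the pilot deliberately not powered for definitive claims. Both statements are correct, and they limit the weight of the point.

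A reader might go further and infer that the 20% is refuted by the team's own pilot rate of under 5%. The documents do not support that. Section 16.2 does not identify the earlier trial as the pilot work behind the 20%; the link is a guess from misnumbered references, and the other prior studies have no stated rate. Nor is planning for a higher loss than one earlier trial saw an error. This protocol counts pregnancy loss and exercise contraindications among its withdrawal grounds (section 3.3.1), and it asks for daily weighing, weekly urine collection and up to six scans (section 6.2.1).

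**Conclusion.** The double allowance is real. Section 15.0 counts drop-out on a figure that already contains it, and the plan gives two different numbers for the randomised cohort: 30 (8.1 and 16.2, consistent with 6.2.1) and an implied 36 (15.0). The size is 6 women: a total of 106 against 100, and about 29 expected completers against 24. The completer figures assume that the plan's own 20% loss applies to everyone randomised.

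A reader might conclude that the sample size of 30 is wrong, or that 24, 30 and 36 are three conflicting stated sizes. Neither follows. N = 30 reproduces exactly. For Study 2, 24 and 36 are only implied (2 × 12 and 30 + 6), and the one written 24, in section 16.2, is the Study 1 target.

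The source of the 20% is a minor, clerical matter. The rate is untraced in the documents, not shown to be false.

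**What to change.** Allow for drop-out once, and give one number randomised in 6.2.1, 8.1, 15.0 and 16.2. There are two ways to do this:

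1. **Delete the 6.** Section 15.0 becomes 30 (already inflated, about 24 completers expected at 20%) + 50 + 20 = 100. If replacement under 3.3.2 is kept, say how it fits within the 30.
2. **Keep the 6 as replacements.** Label it so in 15.0 with a reference to 3.3.2, and state in 8.1 that up to 36 may be randomised, with about 29 completers expected at 20%. The total stays at 106, and 6.2.1 and 16.2 are brought into line.

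In 8.1, also correct the reference numbers and cite the source of the 20%, or describe it as a conservative assumption. The under-5% figure should not be inserted as the source rate, because the documents do not establish that it is.

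The cost is wording only, with no added procedures and no women beyond the 36 that 15.0 already implies. The downside of option 1 is losing an allowance of 6. With 15 per arm, 20% independent losses and no replacement, the chance that one arm keeps at least 12 is 0.648, so for both arms it is 0.648² = 0.42. An arm could well finish slightly under 12.
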